8.3. Safety Analysis

Safety and tolerability of SAGE-718 is the primary objective of this study. Proportion of participants experiencing treatment-emergent adverse events (TEAEs) and severity of TEAEs, number of participants who withdraw due to AEs, and change from baseline in vital signs, clinical laboratory analyses, electrocardiograms (ECGs), and responses on the Columbia–Suicide Severity Rating Scale (C-SSRS) are the primary endpoints.

The Safety Set will be used for all safety summary tables by cohort and overall.

The safety endpoints and variables considered in the summary tables for this study are summarized in [Table 2](#).

Table 2: Safety Endpoints and Variables in the Summary Tables

Safety Evaluation	Incidence	Raw Value	Change from Baseline	Normal Range Shift from Baseline	Potentially Clinically Significant	Abnormality/ Clinical Significance
Adverse Events	X					
Clinical Laboratory (Chemistry, Liver function, Hematology,		X*	X	X	X	

Safety Evaluation	Incidence	Raw Value	Change from Baseline	Normal Range Shift from Baseline	Potentially Clinically Significant	Abnormality/Clinical Significance
Coagulation, Urinalysis)						
Physical Exam		*				
Vital Signs		X	X		X	
ECG		X	X		X	*
C-SSRS	X	X		X		

ECG = Electrocardiograms; C-SSRS = Columbia–Suicide Severity Rating Scale
 X = Safety Assessment will be summarized in tables
 * = Safety Assessment will be listed in individual participant data listings

Anytime on treatment, last value on treatment and last value on study will be included in the summaries whenever indicated in the relevant sections as following: Anytime on treatment is defined as measurement on or after first dose, on or before the date of last dose. Last value on treatment is defined as the last post-baseline value between first dose of IP (exclusive) and up to the date of last dose of IP (inclusive). Last value on study is defined as the last post-baseline value on or after the first dose of IP and on or before the last date of the study.

The safety variables evaluated at scheduled visits are taken as done in nominal visit, without any windowing. If a value is available for a nominal scheduled visit, that value will be used in summary by visit. If scheduled visit value is not available, a value from the specific visit window will be included in summary.

For safety analysis, unscheduled measurements will be included only if a scheduled measurement is not available, and the unscheduled measurement falls within the visit window for the scheduled visit (Table 3). If there are two or more measurements in a visit window, the measurement taken closest to the study day target will be used in analysis. If the two have same distance from the target study day, the latter one will be used.

Table 3: Analysis Visit Window for Safety Analysis

Scheduled Visit	Study Day of Expected Visit	Study Day Window for Visit
Baseline	1	≤ 1
Day 30 (± 7 days)	30	2 to 44
Day 60 (± 7 days)	60	45 to 74
Day 90 (± 7 days)	90	75 to 130

Scheduled Visit	Study Day of Expected Visit	Study Day Window for Visit
Day 180 (± 14 days)	180	131 to 224
Day 270 (± 14 days)	180	225 to 314
Day 365 (± 14 days)	365	315 to 410
Month 15 (± 14 days)	456	411 to 501
Month 18 (± 14 days)	547	502 to 592
Month 21 (± 14 days)	638	593 to 683
Month 24 (± 14 days)	730	684 to 774
Month 27 (± 14 days)	821	775 to 865
Month 30 (± 14 days)	912	866 to 957
Month 33 (± 14 days)	1003	958 to 1048
Month 36 (± 14 days)	1094	1049 to 1139
Month 39 (± 14 days)	1186	1140 to 1231
Month 42 (± 14 days)	1277	1232 to 1321
Month 45 (± 14 days)	1368	1322 to 1413
Month 48 (± 14 days)	1459	≥ 1414

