- ^o Only applicable for direct rollover participants that did not provide sample(s) in the parent study.

- w At scheduled clinic visits, participants will self-administer IP in the clinic under the supervision of study staff. All scheduled safety assessments will be conducted prior to dosing and all scheduled cognitive tests will be administered post dosing. (All Day 1 assessments should be done predose).
- x Study staff will dispense sufficient IP for the participant to take daily at home until the next scheduled visit.
- y Participants will bring all used packaging and unused IP to the clinic at each visit for study staff to review and document.
- z AEs/SAEs will be collected beginning with completion of 718-CIH-301 informed consent through end of study participation. Documented ongoing AE/SAE from parent studies will be collected to follow through resolution.
- aa All medications, supplements, procedures, and therapies taken within 8 weeks prior to obtaining 718-CIH-301 informed consent will be recorded through the end of the study. All medications, supplements, procedures, and therapies used to treat Huntington's Disease or to treat or prevent COVID, regardless of timing will be recorded through the end of the 718-CIH-301 study.

Table 4: Schedule of Assessments: Additional Visits for 718-CIH-301 v2 Completers

Assessments	Re-Qualification Visit ^{a, b}		Post Re-Qualification Safety Check-in
	Up to 28 days prior to Next Scheduled Study Treatment Visit	Next Scheduled Study Treatment Visit (See Table 5) ^c	30 days (± 7 days) after Next Scheduled Study Treatment Visit
Informed re-consent ^d	X		
Reconfirm inclusion/exclusion criteria ^e	X		
Interim medical history ^f	X		
Optional participant training ^g	X		
Body weight	X		
Body height	X		
Vital signs (including orthostatics) ^h	X		X
Physical examination ⁱ	X		X
Serology test ^j	X		
12-lead ECG ^k	X		X
Safety laboratory assessments ^l	X		X
Urine drug test	X		
Alcohol breath test	X		
Cigarette/tobacco use assessment	X		
Pregnancy test ^m	X		
<hr/>			
C-SSRS (Since Last Visit)	X		X
IP self-administration ⁿ			X
IP adherence monitoring			X
AEs/SAEs ^o	X		X
Prior and concomitant medications and procedures/therapies ^p	X		X

Abbreviations: AE = adverse event; C-SSRS = Columbia–Suicide Severity Rating Scale; ECG = electrocardiogram; eCRF = electronic Case Report Form; HIV = human immunodeficiency virus; IP = investigational product; SAE = serious adverse event.

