- ^f Safety laboratory assessments will include blood samples for hematology, biochemistry, coagulation, and urine samples for urinalysis. On dosing days, samples will be collected \leq 2 hours prior to dosing.
- ^g Only applicable for female participants that are not postmenopausal or surgically sterile. For scheduled clinic visits, urine pregnancy tests will be conducted. For remote visits (Months 27, 33, 39, and 45), start and end dates of the last menses will be collected.

- ^p Participants will bring all used packaging and unused IP to the clinic at each in-clinic visit for study staff to review and document.
- ^q Study staff will dispense sufficient IP for the participant to take daily at home until the next scheduled visit. IP will be shipped to the participant's home at remote visits (Months 27, 33, 39, and 45).
- ^r At scheduled clinic visits, participants will self-administer IP in the clinic under the supervision of study staff. All scheduled safety assessments will be conducted prior to dosing and all scheduled cognitive tests will be administered post dosing.
- ^s At remote visits, site staff will check AiCure and query the participant about any missed doses or noncompliance.

Table 6:

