For 718-CIH-301 v2 Completers, interim medical history will be collected from the time of completion of Day 395 under 718-CIH-301 Protocol Version 2 through informed consent for 718-CIH-301 Protocol Version 3 or higher, AEs/SAEs will be collected from the time of informed consent for 718-CIH-301 Protocol Version 3 or higher through end of study participation, and prior and concomitant medications and procedures/therapies will be collected from the time of completion of Day 395 under 718-CIH-301 Protocol Version 2 through end of study participation. Documented ongoing AEs/SAEs and prior and concomitant medications and procedures/therapies from participation under 718-CIH-301 Protocol Version 2 or prior will be followed for resolution through end of study participation.

Participants who have completed Day 365 but not Day 395 under Protocol Version 2

Participants who have completed their Day 365 visit but not their Day 395 visit under Protocol Version 2 when Protocol Version 3 or higher is implemented will NOT be considered “718-CIH-301 v2 Completers”. Instead, these participants will return to the site as soon as possible for a Study Continuation Visit (Appendix 2, Section [20.2](#)) at which they will consent to Protocol Version 3 or higher, complete safety assessments, and be dispensed SAGE-718 to resume study treatment. They will continue study visits per [Table 5](#) and will not have a Day 395 visit.

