8.4. Investigational Product Discontinuation and Early Termination from the Study

A participant may withdraw from the study at any time at his/her own request for any reason. The investigator may discontinue a participant from the study and/or from IP for safety, behavioral, compliance, administrative reasons, or due to pregnancy. Any necessary interruptions to dosing of IP (eg, surgery) will be handled on a case-by-case basis.

The reason for early termination (ET) from the study must be documented in the participant's study record and recorded in the participant's electronic case report form (eCRF).

The Investigator must notify the sponsor and/or the medical monitor when a participant stops participation in the study for any reason.

Participants who discontinue IP early will be invited by the investigator to complete an early termination (ET) visit within 7 days of IP discontinuation and will be asked to return to the clinic for a Safety Follow-Up Visit 30 days (± 7 days) after the ET visit, if possible. The participant will be permanently discontinued from IP (if not previously discontinued) at the ET visit and from the study at the Safety Follow-Up Visit. If the participant does not complete a Safety Follow-Up Visit, they will be permanently discontinued from the study at the ET visit. The Safety Follow-Up Visit will be used to assess AEs and concomitant medications or procedures/therapies;

participants will undergo a urine pregnancy test (females of childbearing potential [FOCBP] only), physical examination, vital signs, C SSRS, [REDACTED].

If the participant withdraws consent for disclosure of future information, the sponsor will retain and continue to use any data collected before such a withdrawal of consent.

If a participant withdraws from the study, he/she may request destruction of any samples taken and not tested, and the investigator must document this in the site study records.

Possible reasons for study discontinuation include but are not limited to the following:

- AE
- Pregnancy
- Protocol deviation
- Non-compliance with study drug
- Lost to follow-up
- Withdrawal by subject
- Screen failure
- Study terminated by sponsor
- Physician decision
- Other

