Abbreviations: ET = early termination; ICH = International Council for Harmonisation of Technical Requirements for Pharmaceuticals for Human Use; IRB = institutional review board; IEC = independent ethics committee; IP = investigational product; [REDACTED]; SAE = serious adverse event; SUSAR = suspected unexpected serious adverse reaction; UK = United Kingdom

20.2. Appendix 2: Study Continuation Visit for Participants Who Completed Day 365 But Not Day 395 Under Protocol Version 2

Participants who have completed their Day 365 visit but NOT their Day 395 visit under Protocol Version 2 and wish to continue participation under Protocol Version 3 or higher will return to the site for the assessments in the table below and then continue on to their Month 15 visit (see [Table 5](#)). The participant's visit schedule should remain relative to the date of their Day 1 visit.

Schedule of Assessments: Study Continuation Visit

Assessments	Study Continuation Visit
	Visit can occur anytime after the Day 365 visit up to Day 395 (± 7 days)
Informed re-consent ^a	X
Body weight	X
Vital signs (including orthostatics) ^b	X
Physical examination ^c	X
Pregnancy test ^d	X
C-SSRS (Since Last Visit)	X
IP dispensation ^e	X
IP self-administration ^f	X
AEs/SAEs	X
Prior and concomitant medications and procedures/therapies	X

Abbreviations: AE = adverse event; C-SSRS = Columbia–Suicide Severity Rating Scale; IP = investigational product; SAE = serious adverse event.

- ^a Both participants and study partners (if applicable) will be re-consented during at the Study Continuation visit. A legally authorized representative may consent on behalf of participants who are not capable of providing informed consent in the opinion of the investigator.
- ^b Vital signs include body temperature, respiratory rate, heart rate, and blood pressure. Vital signs will be measured prior to dosing. Blood pressure and heart rate will be measured after the participant has been in the supine position for at least 5 minutes and then repeated approximately 1 and 3 minutes after standing. Vital signs can be repeated once if out of range.
- ^c Physical examinations will include a brief assessment of general appearance, cardiovascular, respiratory, gastrointestinal, and neurological systems and followed by a targeted physical assessment as needed. A symptom-directed examination may be conducted at any time at the discretion of the investigator.

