Protocol amendment 2 allowed the duration of participation to be extended from up to 1 year to up to 4 years and provided a path to resume treatment for participants who completed study (through Day 395 visit) under Protocol Version 2 ("718-CIH-301 v2 Completers") or

completed treatment (through Day 365 visit) but did not yet have a Day 395 visit. Participants who have completed their Day 395 visit under Protocol Version 2 and wish to continue participation under Protocol Version 3 or higher ("718-CIH-301 v2 Completers") will return to the site for a Re-Qualification Visit up to 28 days prior to resuming IP at their Next Scheduled Study Treatment Visit (relative to the date of their Day 1 visit. Relevant inclusion and exclusion criteria will be re-confirmed at the Re-Qualification Visit, and participants will re-consent to study participation prior to continuing in the study. Thirty (30) days after resuming IP at their Next Scheduled Study Treatment Visit, 718-CIH-301 v2 Completers will return to the site for a Post Re-Qualification Safety Check-in visit to evaluate safety.

Participants who have completed their Day 365 visit but not their Day 395 visit under Protocol Version 2 when Protocol Version 3 or higher is implemented will NOT be considered "718-CIH-301 v2 Completers". Instead, these participants will return to the site as soon as possible for a Study Continuation Visit during which they will consent to Protocol Version 3 or higher, complete safety assessments, and be dispensed SAGE-718 to resume study treatment. They will continue their study visits per in [Table 3](#) and will not have a Day 395 visit.

Figure 1: Study Schematics

Abbreviation: [REDACTED]

^a De novo and gap (>7 days) rollover participants only. For direct (≤7 days) rollover participants, results of selected last parent study assessment to be used as Day 1 assessments when applicable.

^b The Safety Follow-Up Visit will take place 30 days (±7 days) after the Month 48 or ET visit.

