- l Safety laboratory assessments will include blood samples for hematology, biochemistry, coagulation, and urine samples for urinalysis. At the Post Re-Qualification Safety Check-in, samples will be collected \leq 2 hours prior to dosing.
- m Serum pregnancy tests will be conducted for all female participants at the Re-Qualification Visit.
- n At the Post Re-Qualification Safety Check-in, participants will self-administer IP in the clinic under the supervision of study staff. All scheduled safety assessments will be conducted prior to dosing.
- o AEs/SAEs will be collected from the time of informed consent for 718-CIH-301 Protocol Version 3 or higher through end of study participation.
- p All medications, supplements, procedures, and therapies taken after the completion of Day 395 under 718-CIH-301 Protocol Version 2 will be recorded through the end of the study.

Table 8: Schedule of Assessments: Month 15 to Month 48 – All Participants

Assessments	Treatment Period ^a												Safety Follow-Up
	M 15 (±14 d)	M 18 (±14 d)	M 21 (±14 d)	M 24 (±14 d)	M 27 (remote) (±14 d)	M 30 (±14 d)	M 33 (remote) (±14 d)	M 36 (±14 d)	M 39 (remote) (±14 d)	M 42 (±14 d)	M 45 (remote) (±14 d)	M 48 or ET ^b (±14 d)	
Body weight				X				X				X	X
Vital signs (including orthostatics) ^c	X	X	X	X		X		X		X		X	X
Brief physical examination ^d	X	X	X	X		X		X		X		X	X
12-lead ECG ^e		X		X		X		X		X		X	
Safety laboratory assessments ^f	X	X	X	X		X		X		X		X	
Urine drug test		X		X				X				X	
Alcohol breath test		X		X				X				X	
Cigarette/tobacco use assessment				X				X				X	
Pregnancy test ^g	X	X	X	X	X	X	X	X	X	X	X	X	X
C-SSRS (Since Last Visit)	X	X	X	X	X	X	X	X	X	X	X	X	X
UHDRSj													

Assessments	Treatment Period ^a													Safety Follow-Up
	M 15 (±14 d)	M 18 (±14 d)	M 21 (±14 d)	M 24 (±14 d)	M 27 (remote) (±14 d)	M 30 (±14 d)	M 33 (remote) (±14 d)	M 36 (±14 d)	M 39 (remote) (±14 d)	M 42 (±14 d)	M 45 (remote) (±14 d)	M 48 or ET ^b (±14 d)		
IP accountability/return ^p	X	X	X	X		X		X		X		X		
IP dispensation ^q	X	X	X	X	X	X	X	X	X	X	X			
IP self-administration ^r						X (once daily in the morning)								
IP adherence monitoring ^s						X								
AEs/SAEs						X								
Prior and concomitant medications and procedures/therapies						X								

Abbreviations: AE = adverse event; AI = Apathy Inventory;

; C-SSRS = Columbia–Suicide Severity Rating Scale; d = days; ECG = electrocardiogram; ET = early termination;

; IP = investigational product; M = Month; MoCA = Montreal Cognitive

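### The SAP's on-treatment rule assumes one first dose and one last dose, and does not say how it applies to v2 Completers who stopped and later resumed IP

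*SAP*

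**What the plan says.** **Measurements.** SAP 8.3: "Anytime on treatment is defined as measurement on or after first dose, on or before the date of last dose". Last value on treatment is bounded by the same first and last dose.

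**AEs.** SAP 8.3.1 treats an AE as on-treatment from the first dose to 30 days after the last dose, and as post-treatment from 31 days after it.

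**The break in dosing.** SAP 5.1 says that Protocol amendment 2 also gave a route back to participants who "completed treatment (through Day 365 visit) but did not yet have a Day 395 visit", so Version 2 treatment ended at Day 365. Those who had also completed Day 395, the v2 Completers, resume at their next scheduled treatment visit. The first visit in Protocol Table 5 is Month 15.

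**Data collected inside the break.**
- Protocol Table 4 places a Re-Qualification Visit with labs, ECG and vital signs at this time: "Up to 28 days prior to Next Scheduled Study Treatment Visit".
- At the resumption visit, Protocol Table 5 requires: "All scheduled safety assessments will be conducted prior to dosing and all scheduled cognitive tests will be administered post dosing".
- For v2 Completers, Protocol 7.1.3.1 says: "AEs/SAEs will be collected from the time of informed consent for 718-CIH-301 Protocol Version 3 or higher through end of study participation". Consent is taken at the Re-Qualification Visit.

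**Where the labels are used.** They appear in the pre/on/post-treatment line of the overall TEAE summary (SAP 8.3.1), the anytime and last-value rows for labs and ECG (SAP 8.3.2, 8.3.3) and the last-value rows for vital signs (SAP 8.3.4). SAP 6.1 says that the report focuses on Day 1, Day 90, Day 180, Day 365 and ET.

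**The concern.** A participant with two dosing periods has two first doses and two last doses, and the SAP does not say which pair the definitions use. The gap is part of the design for v2 Completers, and safety data are collected within it. A row headed on treatment could therefore mix on-drug values with values taken weeks or months after the previous dose. The label of an AE arising in the gap would depend on whether the person later resumed. Safety and tolerability are the primary objective, so these labels should mean what they say.

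**Working it through.** **Inputs**
- Last Version 2 dose at the Day 365 visit (SAP 5.1). The Version 2 schedule is not in the documents, so the current ±14-day window is assumed: Days 351 to 379.
- Resumption targets T from SAP Table 3: Day 456 (Month 15), 547 (Month 18) and 638 (Month 21), each ±14 days.
- Re-Qualification 0 to 28 days before resumption (Protocol Table 4).
- Day 395 visit no later than Day 395 + 7 = 402. The ±7 is taken from Protocol Appendix 2 and assumed to apply to the Version 2 visit.
- AE tail of 30 days (SAP 8.3.1).

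**Length of the gap.** Nominal = T − 365; shortest = (T − 14) − 379; longest = (T + 14) − 351. Re-Qualification falls from gap − 28 to gap days after the last Version 2 dose.

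| Resumption | Nominal gap | Shortest | Longest | Re-Qualification, nominal | Re-Qualification, earliest |
|---|---|---|---|---|---|
| Month 15 | 456 − 365 = 91 | 442 − 379 = 63 | 470 − 351 = 119 | 63 to 91 | 63 − 28 = 35 |
| Month 18 | 547 − 365 = 182 | 533 − 379 = 154 | 561 − 351 = 210 | 154 to 182 | 154 − 28 = 126 |
| Month 21 | 638 − 365 = 273 | 624 − 379 = 245 | 652 − 351 = 301 | 245 to 273 | 245 − 28 = 217 |

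These are differences between dose dates; days without a dose are one fewer. The smallest Re-Qualification figure, 35 days, already exceeds the 30-day AE tail.

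**AEs, Month 15 resumption, nominal days.** After a last Version 2 dose at Day 365:
- Days 366 to 395 are on-treatment under the 30-day tail, and post-treatment starts at Day 396.
- Version 3 consent is no earlier than Day 456 − 28 = 428. AEs on Days 428 to 455 (28 days) begin 63 to 90 days after that dose.
- Version 2 AEs on Days 396 to 402 (up to 7 days) are also past the tail. With a last dose at Day 351 the tail ends at Day 381, and Days 382 to 402 give up to 21 days.
- Other new events between Day 395 and Version 3 consent go to interim medical history (Protocol Table 4), so they do not enter.

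With the final dose as last dose, all of these AEs are on-treatment. Had the person not resumed, those in the Version 2 tail would be post-treatment.

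**The other reading.** If the Version 2 last dose is used, resumption at Day 456 comes 91 days after it. Every AE on resumed drug becomes post-treatment, and every resumed lab or ECG falls outside anytime on treatment.

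**Values.** Counting only the schedules available, with Re-Qualification and resumption on different days, a Month 15 resumer has two planned off-drug lab sets and one ECG. A Month 18 resumer has two of each, because SAP Table 8 ("Schedule of Assessments: Month 15 to Month 48") has an ECG at Month 18 but not at Month 15. Anything measured at the Version 2 Day 395 visit would be extra, and sooner after the last dose than 35 days.

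**Last value on treatment.** A gap value can take this role only if no later value exists on or before the final dose. The first planned on-drug assessment after resumption is at 30 ± 7 = 23 to 37 days.

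**Table 3.** The Day 270 row has target 180 and window 225 to 314. Every day in the window lies above 180, so the closest-to-target rule picks the earliest value: |226 − 180| = 46 beats |270 − 180| = 90.

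**The case against.** **The last dose is undefined, so no consequence is certain.** This stands. The final-dose reading is the natural one, but the SAP does not state it. Each reading mislabels something, so the definition needs repair either way.

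**SAP 6.1 may remove the lab, ECG and vital-sign rows.** This stands as a possibility. The anytime and last-value rows are not visits, and SAP 8.3.2 to 8.3.4 still ask for them, but 6.1 does not say whether its list restricts them. If it does, only the AE line remains.

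**Dosing dates are listed anyway.** SAP 8.2.5 lists first and last intake and interruption dates, and SAP 8.2.1 counts interruptions. Neither is tied to the on-treatment rule, and the documents do not say that the Version 2-to-3 gap is recorded as an interruption.

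**An ET value would normally replace a gap value.** Largely true. Protocol 8.4 says: "The participant will be permanently discontinued from IP (if not previously discontinued) at the ET visit". Values dated on the last-dose day displace a gap value; ET values taken after the last dose do not.

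**Stronger readings that the documents do not support**
- A reader might infer that the main safety results are distorted. The any-TEAE proportion, SOC/PT tables, liver PCS (anytime post-baseline), C-SSRS and nominal-visit summaries do not use the span.
- A reader might treat the planned lab and ECG counts above, or 28 AE-days, as per-person totals. The Version 2 Day 395 assessments and late Version 2 AEs lie outside those figures.
- A reader might extend the point in full to Study Continuation participants. For that visit, "Visit can occur anytime after the Day 365 visit up to Day 395" plus 7 days gives a gap of at most 402 − 365 = 37 days (402 − 351 = 51 with windows), and it has no labs or ECG. At most 6 AE-days (Days 396 to 401), or 20 (Days 382 to 401), pass the 30-day tail.
- A reader might want to bar unscheduled off-drug values from filling a missing visit. The by-visit tables are not labelled on-treatment, so this does not follow.

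**Conclusion.** The point holds, as a minor one. The definitions in SAP 8.3 and 8.3.1 do not fit participants with two dosing intervals, and no analysis section adapts them. The 35-day minimum assumes a last Version 2 dose at the Day 365 visit and visits in window, and covers only Re-Qualification and resumption values. The AE mislabelling is up to 28 days between Version 3 consent and resumption, plus any Version 2 AEs from 31 days after the last Version 2 dose up to the Day 395 visit.

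The certain reach is one line of the overall TEAE summary in a purely descriptive, single-treatment report. The supplementary rows are affected only if SAP 6.1 leaves them in. Neither the number of resumers nor the Version 2 Day 395 assessments are given, so total counts and the overall effect cannot be computed. No direction of bias is claimed. The Day 270 target is a separate slip at a visit outside the five in SAP 6.1, and matters only when no scheduled value exists.

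**What to change.** In SAP 8.3 and 8.3.1:
- Define first and last dose for each dosing interval.
- Values: on treatment from first to last dose of each interval, with pre-dose values at the resumption visit assigned to the gap.
- AEs: on-treatment from first dose to last dose + 30 days of each interval. From last dose + 31 days until resumption they are post-treatment for the first interval.
- State whether the five visits in SAP 6.1 restrict the anytime and last-value rows.

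Separately, change the Day 270 target in SAP Table 3 from 180 to 270.

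The cost is SAP wording, one table cell and a dosing-interval flag in the programming. If the gap was not recorded as an IP interruption, the last Version 2 dose date and the resumption date must come from the dosing records. No new data are needed.
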